7.0 TRIAL PROCEDURES

7.1 Trial Procedures

The Trial Flow Chart in Section 6.0 summarizes the trial procedures to be performed at each visit. Individual trial procedures are described in detail below. It may be necessary to perform these procedures at unscheduled time points if deemed clinically necessary by the investigator.

Furthermore, additional evaluations/testing may be deemed necessary by the investigator and/or Merck for reasons related to subject safety. In some cases, such evaluation/testing may be potentially sensitive in nature (e.g., HIV, Hepatitis C, etc.), and thus local regulations may require that additional informed consent be obtained from the subject. In these cases, such evaluations/testing will be performed in accordance with those regulations.

7.1.1 Administrative Procedures

7.1.1.1 Informed Consent

The investigator must obtain documented consent from each potential subject prior to participating in a clinical trial.

7.1.1.1.1 General Informed Consent

Consent must be documented by the subject's dated signature or by the subject's legally acceptable representative's dated signature on a consent form along with the dated signature of the person conducting the consent discussion.

A copy of the signed and dated consent form should be given to the subject before participation in the trial.

The initial informed consent form, any subsequent revised written informed consent form and any written information provided to the subject must receive the IRB/ERC's approval/favorable opinion in advance of use. The subject or his/her legally acceptable representative should be informed in a timely manner if new information becomes available that may be relevant to the subject's willingness to continue participation in the trial. The communication of this information will be provided and documented via a revised consent form or addendum to the original consent form that captures the subject's dated signature or by the subject's legally acceptable representative's dated signature.

Specifics about a trial and the trial population will be added to the consent form template at the protocol level.

The informed consent will adhere to IRB/ERC requirements and applicable laws and regulations.

7.1.1.2 Inclusion/Exclusion Criteria

All inclusion and exclusion criteria will be reviewed by the investigator or qualified designee to ensure that the subject qualifies for the trial.

7.1.1.3 Medical History

A medical history will be obtained by the investigator or qualified designee. Medical history will include all active conditions, and any condition diagnosed within the prior 10 years that are considered to be clinically significant by the investigator. Details regarding the disease for which the subject has enrolled in this study will be recorded separately and not listed as medical history.

7.1.1.4 Prior and Concomitant Medications Review

7.1.1.4.1 Prior Medications

The investigator or qualified designee will review prior medication use, including any protocol-specified washout requirement, and record prior medication taken by the subject within 28 days before starting the trial. The subject will not have received prior treatment for the disease.

7.1.1.4.2 Concomitant Medications

The investigator or qualified designee will record medication, if any, taken by the subject during the trial. All medications related to reportable SAEs and ECIs should be recorded as defined in Section 7.2.

7.1.1.5 Disease Details and Treatments

7.1.1.5.1 Disease Details

The investigator or qualified designee will obtain prior and current details regarding disease status.

7.1.1.5.2 Subsequent Anti-Cancer Therapy Status

The investigator or qualified designee will review all new anti-neoplastic therapy initiated after the last dose of trial treatment.

7.1.2 Clinical Procedures/Assessments

7.1.2.1 Adverse Event (AE) Monitoring

The investigator or qualified designee will assess each subject to evaluate for potential new or worsening AEs as specified in the Trial Flow Chart and more frequently if clinically indicated. Adverse experiences will be graded and recorded throughout the study and during the follow-up period according to NCI CTCAE Version 4.0 (see Section 11.2). Toxicities will be

characterized in terms regarding seriousness, causality, toxicity grading, and action taken with regard to trial treatment.

For subjects receiving treatment with pembrolizumab all AEs of unknown etiology associated with pembrolizumab exposure should be evaluated to determine if it is possibly an event of clinical interest (ECI) of a potentially immunologic etiology (termed immune-related adverse events, or irAEs); see the separate ECI guidance document in Appendix 11.3.10 regarding the identification, evaluation and management of potential irAEs.

Please refer to section 7.2 for detailed information regarding the assessment and recording of AEs.

7.1.2.2 Physical Exam

The investigator or qualified designee will perform a complete physical exam during the screening period. Clinically significant abnormal findings should be recorded as medical history. A physical exam should be performed during screening.

7.1.2.3 Vital Signs

Vital signs will be taken at screening, prior to the administration of each dose of trial treatment and at treatment discontinuation as specified in the Trial Flow Chart (Section 6.0). Vital signs should include temperature, pulse, respiratory rate, weight and blood pressure. Height will be measured at screening only.

7.1.2.4 Eastern Cooperative Oncology Group (ECOG) Performance Scale

The investigator or qualified designee will assess ECOG status (see Section 11.1) at screening, prior to the administration of trial treatment, and after discontinuation of trial treatment as specified in the Trial Flow Chart.

7.1.2.5 Tumor Imaging and Assessment of Disease

Tumor imaging and assessment of disease will be performed according to each disease subtype:

7.1.2.5.1 Follicular lymphoma

FDG-PET imaging will be required during study screening and prior to treatment on cycle 7 to determine candidacy for continuation on study. Contrast-enhanced computed tomography (CT) of the chest, abdomen, and pelvis alone will be performed at each tumor assessment. For measurement of response, 2014 criteria as described in “Recommendations for Initial Evaluation, Staging, and Response Assessment of Hodgkin and Non-Hodgkin Lymphoma: The Lugano Classification” will be used (see Appendix 11.3.1) (18). CT imaging of the neck will be performed as indicated for standard of care.

All CT scans should be performed with IV contrast unless contraindicated, and abdominal and pelvis scans should be performed with oral contrast.

7.1.2.5.2 Marginal Zone Lymphoma in which Nodal Disease is Known or Suspected

CT of the chest, abdomen, and pelvis will be performed at each tumor assessment. For measurement of response, 2014 criteria as described in “Recommendations for Initial Evaluation, Staging, and Response Assessment of Hodgkin and Non-Hodgkin Lymphoma: The Lugano Classification” will be used (see Appendix 11.3.2) (18). CT imaging of the neck will be performed as indicated for standard of care.

All CT scans should be performed with IV contrast unless contraindicated, and abdominal and pelvis scans should be performed with oral contrast.

7.1.2.6 Bone marrow aspirate and biopsy

A bone marrow aspirate and biopsy will be obtained before the first dose of study drug, and for confirmation of CR when indicated. Bone marrow aspirate and biopsy requirements may be waived by the Sponsor-Investigator or lead sub-Investigator. These samples will be evaluated locally.

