6.0 TRIAL FLOW CHART

6.1 Study Flow Chart

	Screening Period	Treatment Phase			End of treatment ⁶	Long-term Follow-up ⁷
		Window Cycles (1-6)	Response assessment ⁸	Continuation Cycles (7-18) ⁹		
Scheduling and Timing	-42 to -1d	+/- 3d		+/- 3d		
Informed consent	X					
Inclusion/Exclusion criteria	X					
Medical history	X					
Medication review (prior and concomitant)	X	X		X		
Trial treatment administration		X		X		
Post-study anticancer therapy status						X
Survival status						X
Vital signs	X	X		X	X	
Physical exam	X	X		X	X	
ECOG performance status	X	X		X	X	
Adverse event assessment ¹	X	X		X	X	
CBC and differential	X	X	X	X	X	
Comprehensive metabolic panel and LDH	X	X	X	X	X	
HepB SAg, Hep B Core Ab, HepC Antibody and HIV screen	X					
Urinalysis	X					
T3, FT4, and TSH	X	X		X	X	
PT/INR and aPTT	X					
Correlative studies blood draw	X		X		X	
Bone marrow studies ²	X					X
Pregnancy test ³	X					
Tumor assessment ⁵	X	X	X	X	X	
Archival Tissue collection ⁴	X					

¹Adverse events will be recorded from the time of a subject signing consent up until 30 days after the last dose of pembrolizumab, or 90 days after the last dose of pembrolizumab in the case of serious adverse events.

²If bone marrow involvement by iBCL was previously shown then repeat bone marrow exam at screening is not required as it is assumed positive. Otherwise, bone marrow studies include aspirate and unilateral biopsy and should be performed at screening unless a waiver is approved by the study Sponsor-Investigator or sub-Investigator. If all bone marrow studies are negative at screening, these do not need to be repeated. If bone marrow status is unknown or positive at screening, patients will need to have bone marrow study for confirmation of a CR.

³Pregnancy test is only required in women of childbearing potential.

⁴Archived tumor samples are requested for pathologic confirmation and biomarker analysis. If an archived specimen is not available or contains insufficient material, a fresh tumor biopsy (if clinically feasible) will be requested. Correlative studies may be performed on any available tissue.

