11.3 Response Evaluation

11.3.1 The Lugano Response Classification: For FL and MZL (18)

Response and Site	PET-CT-Based Response	CT-Based Response
Complete	Complete metabolic response Score 1, 2, or 3* with or without a residual mass on 5PS [†] It is recognized that in Waldeyer's ring or extranodal sites with high physiologic uptake or with activation within spleen or marrow (eg, with chemotherapy or myeloid colony-stimulating factors), uptake may be greater than normal mediastinum and/or liver. In this circumstance, complete metabolic response may be inferred if uptake at sites of initial involvement is no	Complete radiologic response (all of the following) Target nodes/nodal masses must regress to ≤ 1.5 cm in LD _i No extralymphatic sites of disease
Lymph nodes and extralymphatic sites		

Response and Site	PET-CT-Based Response	CT-Based Response
	greater than surrounding normal tissue even if the tissue has high physiologic uptake	
Nonmeasured lesion	Not applicable	Absent
Organ enlargement	Not applicable	Regress to normal
New lesions	None	None
Bone marrow	No evidence of FDG-avid disease in marrow	Normal by morphology; if indeterminate, IHC negative
Partial	Partial metabolic response	Partial remission (all of the following)
Lymph nodes and extralymphatic sites	Score 4 or 5 [†] with reduced uptake compared with baseline and residual mass(es) of any size	≥ 50% decrease in SPD of up to 6 target measurable nodes and extranodal sites
	At interim, these findings suggest responding disease	When a lesion is too small to measure on CT, assign 5 mm × 5 mm as the default value
	At end of treatment, these findings indicate residual disease	When no longer visible, 0 × 0 mm
		For a node > 5 mm × 5 mm, but smaller than normal, use actual measurement for calculation
Nonmeasured lesions	Not applicable	Absent/normal, regressed, but no increase
Organ enlargement	Not applicable	Spleen must have regressed by > 50% in length beyond normal
New lesions	None	None
Bone marrow	Residual uptake higher than uptake in normal marrow but reduced compared with baseline (diffuse uptake compatible with reactive changes from chemotherapy allowed). If there are persistent focal changes in the marrow in the context of a nodal response, consideration should be given to further evaluation with MRI or biopsy or an interval scan	Not applicable
No response or stable disease	No metabolic response	Stable disease

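### Section 7.1.2.6 lets the marrow exam that confirms CR be waived without limit, footnote 2 of the flow chart limits the waiver to screening, and no rule classifies an imaging CR without marrow evidence

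*Combined protocol and SAP*

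**What the plan says.** Section 7.1.2.6 sets two marrow requirements: "A bone marrow aspirate and biopsy will be obtained before the first dose of study drug, and for confirmation of CR when indicated". The next sentence but one to the end of that short section reads "Bone marrow aspirate and biopsy requirements may be waived by the Sponsor-Investigator or lead sub-Investigator". It names no time point, gives no criteria and asks for no record of the waiver.

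Footnote 2 of the flow chart (section 6.1) is narrower. Its waiver is tied to the baseline exam, which "should be performed at screening unless a waiver is approved by the study Sponsor-Investigator or sub-Investigator". Marrow already known to be involved need not be re-examined at screening and is assumed positive. For response the footnote says: "If bone marrow status is unknown or positive at screening, patients will need to have bone marrow study for confirmation of a CR". It allows no exception to that.

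The response criteria are in appendix 11.3.1. For CR, the marrow row of the CT column reads "Normal by morphology; if indeterminate, IHC negative", and the same row of the PET-CT column reads "No evidence of FDG-avid disease in marrow".

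The imaging differs by histology. For follicular lymphoma (section 7.1.2.5.1), "FDG-PET imaging will be required during study screening and prior to treatment on cycle 7 to determine candidacy for continuation on study", with CT at each tumor assessment. For marginal zone lymphoma (section 7.1.2.5.2), "CT of the chest, abdomen, and pelvis will be performed at each tumor assessment", and no PET is required.

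The CR rate is named as a secondary outcome in section 3.2. The primary endpoint in section 8.3.1 is CR plus PR among all treated patients.

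**The concern.** Two current rules disagree on whether the marrow exam that confirms CR can be dispensed with. Under section 7.1.2.6 it can, at the discretion of the trial's own leadership. Under footnote 2 it cannot, for anyone whose screening marrow was positive or unknown.

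The two waivers can also compound. Waiving the screening exam can leave marrow status unknown, which is one of the two groups that footnote 2 says must be examined before CR is confirmed. If the second exam is waived as well, the marrow is never looked at. A patient assumed positive at entry could likewise have the clearance exam waived.

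No section says how to classify the response in that situation. A reader of the reported CR rate could not tell which CRs met the protocol's own confirmation requirement. Any resulting error runs one way: omitting the exam can keep a patient in the CR category but cannot remove one from it.

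**Working it through.** **1. The plan's design figure.** Inputs from section 8.2: null ORR 25%, alternative 50%, one-sided 0.05, stop at 4 or fewer responses in 16, success at 13 or more in 33.

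P(success | p) = Σ over x = 5 to 16 of b(16, x, p) × P[Bin(17, p) ≥ 13 − x]

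- At p = 0.50: 0.902. The stated 90% reproduces.
- At p = 0.25: 0.045, below the 0.05 limit.

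These depend only on the number of responders (CR + PR). Moving a patient from CR to PR leaves both figures and both boundaries unchanged.

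**2. The rules side by side.**

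| Question | Section 7.1.2.6 | Footnote 2, section 6.1 |
|---|---|---|
| May the screening exam be waived? | Yes | Yes |
| May the CR-confirming exam be waived? | Yes: the waiver follows both requirements and is not limited | No: needed if screening marrow is unknown or positive |
| Class if that exam is missing | Not stated | Not stated |

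**3. Where the response criteria are affected.** Take a patient with unknown or positive screening marrow, CR on imaging and no later marrow exam.

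- *Marginal zone lymphoma, CT.* The CT column needs normal marrow morphology, so the appendix requirement is not shown to be met. Footnote 2 is not met either.
- *Follicular lymphoma read on CT only.* Same position.
- *Follicular lymphoma with PET before cycle 7.* The PET-CT column asks only for no FDG-avid marrow disease, so the appendix can be satisfied without a biopsy. Footnote 2 is still not met, because it does not distinguish histology or imaging.

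**4. Does ORR move?** On CT, marrow is not applicable to PR, so an unconfirmed CR will normally still be PR and remain a responder. There is a rare exception. Entry needs only a lesion above 1.5 cm, and the CR nodal limit is 1.5 cm. A hypothetical single node going from 1.8 × 1.5 cm to 1.5 × 1.3 cm meets the CR nodal limit, but its product falls from 2.70 to 1.95 cm²: (2.70 − 1.95)/2.70 = 28%, short of the 50% needed for PR. Without marrow confirmation that patient would be SD.

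**5. Size on the CR rate.** Each patient moves it by 1/33 = 3.0 percentage points.

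For illustration, assume 6 imaging CRs among 33, of whom 2 to 4 have unknown or positive screening marrow. The documents give no such counts. Intervals are exact 95%.

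| Case | CR rate | 95% interval |
|---|---|---|
| All six counted | 6/33 = 18.2% | 7.0 to 35.5 |
| Two not confirmed | 4/33 = 12.1% | 3.4 to 28.2 |
| Four not confirmed | 2/33 = 6.1% | 0.7 to 20.2 |

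The lower rows apply only if every one of those marrows is positive or never obtained. If all are done and negative, the rate stays at 18.2%.

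**The case against.** The strongest reply is that section 7.1.2.6 waives a procedure and leaves the response criteria alone. Sections 7.1.2.5.1 and 7.1.2.5.2 adopt the Lugano criteria, and the CT column requires all its conditions for CR. Read strictly, a patient assessed on CT whose marrow was needed and never examined does not meet CR, whatever was waived. This stands in part. A reader might infer that the plan provides for waived cases to be recorded as CR, but no section says that a waived marrow counts as negative. What remains is that no rule settles the case, and the broader waiver leaves room for either classification.

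A reader might also infer that the waiver is a decision taken by unblinded leadership once the scan is known. That timing is likely, since the exam arises only when imaging suggests CR, but it is not stated, and a waiver could be agreed in advance. Lack of blinding is common to any open-label single-arm trial and is not a separate fault.

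Nor is it right to say that every patient with positive screening marrow could be called CR without evidence of clearance. For follicular lymphoma before cycle 7, PET is the marrow evidence that the appendix specifies.

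Finally, little depends on the CR rate. Section 8.3.2 gives it no hypothesis, threshold or analysis of its own. Duration of response starts at the first CR or PR, and continuation under section 7.1.5.2 rests on objective response or stable disease. This stands and limits the weight of the point.

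**Conclusion.** The contradiction between section 7.1.2.6 and footnote 2 is real, applies to both histologies and should be reconciled. The further mismatch with appendix 11.3.1 is mainly for marginal zone lymphoma and for follicular lymphoma assessments read on CT only.

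The consequence is a possible upward error of 3.0 percentage points per patient in a descriptive secondary rate, assuming 33 treated patients. How many patients would be affected cannot be taken from the documents, so a fall from 18% to between 6% and 12% is a worst-case illustration on assumed counts and not an estimate.

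A reader might infer that the primary result is at risk. The documents do not support that: the Simon boundaries, type I error and power are unchanged, and ORR could differ only where an unconfirmed CR also fails the PR criteria.

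**What to change.** In section 7.1.2.6, state that the waiver applies to the screening exam as in footnote 2. Add that, for response classification, a subject with unknown or positive screening marrow and no negative post-baseline marrow is not counted as a confirmed CR. Then give the default class:

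- **CT-based assessment:** PR if the PR criteria are met, otherwise SD.
- **PET complete metabolic response:** report as *CR, marrow unconfirmed*, keep as a responder in ORR, and leave out of the confirmed CR rate.

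A blanket rule assigning PR would not work. A complete metabolic response (score 1 to 3) does not meet the PET definition of PR, which needs a score of 4 or 5, and a small node can reach 1.5 cm without the 50% fall that CT-based PR requires.

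Report the number of waived marrows, and give the CR rate with and without unconfirmed cases.

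The cost is protocol wording and one extra line in the results. No biopsy is forced, and no sample size or decision boundary changes. The downside is that some true CRs without a marrow will not be counted, so the confirmed CR rate may be slightly lower.

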7.1.2.7 Tumor Tissue Collection and Correlative Studies Blood Sampling

Assessment of available archived tumor tissue for correlative study analysis will be performed during the screening period. Available pretreatment biopsy tissue will be provided for correlative study analysis. Peripheral blood correlative study samples will be collected during screening, at response assessment, and at end-of-treatment (see Section 6.1).

Specimen Requirements

- A 5-10 mL specimen of peripheral blood in a lavender- (EDTA) or green- (sodium heparin) tube is acceptable for each draw.
- Storage/Transport Temperature: Specimens can be transported with a cold pack or wet ice, but do not fix or freeze specimens.
- Unacceptable Conditions: Frozen specimens, specimens greater than 48 hours old, specimens fixed in formalin for flow cytometry.

Address for shipping specimens:

Seattle Cancer Care Alliance
Hematopathology Laboratory G7800
[name]
[name]

7.1.3 Laboratory Procedures/Assessments

Details regarding specific laboratory procedures/assessments to be performed in this trial are provided below and in Section 6.1. All chemistry and hematology studies may be performed within 3 days of pembrolizumab dosing prior to day 1 of each cycle.

Laboratory tests for hematology, chemistry, urinalysis, and others are specified in Table 5.

Table 5 Laboratory Tests

Hematology	Chemistry	Urinalysis	Other
Hematocrit	Albumin	Blood	Serum β -human chorionic gonadotropin†
Hemoglobin	Alkaline phosphatase	Glucose	(β -hCG)†
Platelet count	Alanine aminotransferase (ALT)	Protein	PT (INR)
WBC (total and differential)	Aspartate aminotransferase (AST)	Specific gravity	aPTT
Red Blood Cell Count	Lactate dehydrogenase (LDH)	Microscopic exam (If abnormal)	Total triiodothyronine (T3)
Absolute Neutrophil Count	Carbon Dioxide ‡	results are noted	Free tyroxine (T4)
Absolute Lymphocyte Count	(CO_2 or bicarbonate)	Urine pregnancy test †	Thyroid stimulating hormone (TSH)
	Uric Acid		Hepatitis B Surface Antigen (HBsAg)
	Calcium		Hepatitis B Core Antibody (HBcAb)
	Chloride		Hepatitis C Antibody
	Glucose		HIV Screening
	Phosphorus		PK
	Potassium		Blood for correlative studies
	Sodium		
	Magnesium		
	Total Bilirubin		
	Direct Bilirubin (If total bilirubin is elevated above the upper limit of normal)		
	Total protein		
	Blood Urea Nitrogen		

† Perform on women of childbearing potential only. If urine pregnancy results cannot be confirmed as negative, a serum pregnancy test will be required.

‡ If considered standard of care in your region.

Results must be reviewed by the investigator or qualified designee and found to be acceptable prior to each dose of trial treatment.

7.1.4 Other Procedures

7.1.4.1 Withdrawal/Discontinuation

When a subject discontinues/withdraws prior to trial completion, all applicable activities scheduled for the final trial visit should be performed at the time of discontinuation. Any adverse events which are present at the time of discontinuation/withdrawal should be followed in accordance with the safety requirements outlined in Section 7.2 - Assessing and Recording Adverse Events.

